9.1. Adverse Events

An AE is defined as any untoward medical occurrence associated with the use of a drug in humans, whether or not considered drug related.

A treatment-emergent AE (TEAE) is defined as any event not present before exposure to study drug or any event already present that worsens in intensity or frequency after exposure. Adverse events will also be evaluated by the investigator for the coexistence of medically attended AE which is defined as an AE that leads to an unscheduled visit to a healthcare practitioner.

Adverse events will be coded by preferred term (PT) and system organ class (SOC) using Medical Dictionary for Regulatory Activities (MedDRA) and summarized by treatment group as defined in Section 5, vaccination (first or second), and overall.

All summary tables (except for the overall summary of AEs) will present SOC and PT, will include counts of subjects, and will be based on TEAEs. System organ class will be displayed in descending order of overall frequency and then alphabetically. Preferred term will be displayed in descending order of overall frequency and then alphabetically within SOC. Percentages will be based upon the number of subjects in the Safety set within each treatment group as defined in Section 5.

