All AEs necessitating an unscheduled physician visit, medical attention, or leading to withdrawal from the study will also be collected throughout Part A of the study, and all AEs will be monitored until resolution or, if the AE becomes chronic, a cause is identified. If an AE is unresolved at the conclusion of Part A of the study, a clinical assessment will be made by the investigator and the medical monitor to determine whether or not continued follow-up of the AE is warranted. The relationship of the study drug to any AE and any SAE will be determined by the investigator as related or not related. All AEs resulting in withdrawal of the subjects from the study will be documented in the source documents and in the eCRF.

For Part B of the study, a script will be utilized to query for any new SAEs or AESIs and proper documentation will be obtained to allow an assessment of relatedness to vaccination or study

participation. All SAEs and AESIs will be followed to resolution, to chronic stable state, or until the last subject visit for Part B occurs. At that time, any ongoing AEs will receive their final classification so that the safety database can be locked.

A tabulation of all SAEs and AESIs, categorized by the Medical Dictionary for Regulatory Activities (MedDRA) preferred terms and assessed relationship to study drug, will be performed.

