### **3.5.7.2 Eliciting and Documenting Adverse Events**

The investigator is responsible for ensuring that all AEs and SAEs are recorded in the eCRF and reported to Moderna Therapeutics, Inc. In Part A of the study, AEs will be assessed from the time of the first dose administration at Visit 1 through Visit 7. However, for the time period after the ICF is signed until before receiving the study drug, AEs will only be recorded when they are defined as one or more of the following: SAEs, AESIs, or AEs leading to study withdrawal. In Part B of the study, AESIs and SAEs will be assessed from Visit 8 through Visit 19. Any AEs occurring before receipt of the study drug will be analyzed separately from TEAEs.

At every clinic visit or telephone contact, subjects will be asked a standard question to elicit any medically related changes in their well-being according to the scripts provided. Subjects will also be asked if they have been hospitalized, had any accidents, used any new medications, or changed concomitant medication regimens (both prescription and over-the-counter medications).

In addition to subject observations, data from clinical laboratory test results, physical examination findings, or other documents relevant to subject safety classified as an AE will be documented on the AE page of the eCRF.

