### **3.6.5.2      Safety Analyses**

Data for subjects receiving placebo will be pooled across all dose levels for all presentations. Reactogenicity will be summarized by dose levels (25, 50, or 100 µg or placebo), vaccination (first or second), duration, relationship to study vaccine, and severity. Adverse events will be coded by preferred term and system organ class using MedDRA and summarized by part, treatment, vaccination (first or second), and overall. Adverse events will also be summarized by severity and relationship to study vaccine. Descriptive statistics will be presented and the difference in the proportion of AEs will be provided comparing each dose level with placebo recipients pooled across all dose levels. Adverse events for subjects in the safety cohort for each dose level will be provided in a separate subject listing. Adverse events leading to withdrawal, AESIs, medically attended AEs, and SAEs will be provided by subject in a listing.

Safety data from clinical laboratory test results and vital sign measurements will be graded by severity and analyzed by treatment group and vaccination (first or second). Absolute and change from baseline values will be provided according to the toxicity table, along with mean, median, and standard deviation. Results of hematology, serum chemistry, coagulation, and urinalysis assessments; urine drug screen; and pregnancy testing will be listed for all subjects randomly assigned to receive study treatment.

Medical history data for all subjects randomly assigned to receive study treatment will be presented by subject in a listing.

Baseline demographic and background variables will be summarized by treatment group and cohort for all subjects. The number of subjects who enroll in the study and the number and percentage of subjects who complete the study will be presented. Frequency and percentage of subjects who withdraw or discontinue from the study, and the reason for withdrawal or discontinuation, will also be summarized.

Prior and concomitant medication will be listed (with start and stop dates) for each subject and summarized by common medical dictionary coding. Any vaccinations that occur during the trial conduct will also be captured and summarized.

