9.1.1. Incidence of Adverse Events

Individual subject listings will be provided for all AEs, AEs leading to withdrawal, AESIs, medically attended AEs.

An overall summary of AEs will be created to include the number and percentage of subjects who experience the following:

- Any unsolicited AE (Part A)
- Any unsolicited treatment-related AE (Part A)
- Any unsolicited AE of grade 3 or 4 (Part A)
- Any unsolicited treatment-related AE of grade 3 or 4 (Part A)
- Any SAE (Part A)

- Any treatment-related SAE (Part A)
- Death (Part A)
- Any AEs leading to withdrawal (Part A)
- Any AE of special interest (Part A)
- Any medically-attended AE (Part A)
- Any SAE (Part B)
- Any treatment-related SAE (Part B)
- Death (Part B)
- Any AEs leading to withdrawal (Part B)
- Any AE of special interest (Part B)

The AEs in Part A will be the AEs that started on or before Visit 7. The AEs in Part B will be the AEs that started after Visit 7.

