9.1.6. Adverse Events of Special Interest

Certain AESIs are evaluated after the administration of immunostimulatory agents. All subjects enrolled in the study will be monitored for AESIs from enrollment through the EOS visit. The occurrence of any of these AEs will be treated as an SAE, meeting the criterion of a “medically important event.” The list of AESIs is presented in Section 6.2 of the Protocol. The AESI diagnosis, as well as any medications taken to treat the condition, will be recorded in the subject’s eCRF.

All AESIs will be presented in a data listing.

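### The SAP's SOC/PT adverse-event tables omit the protocol's split by study part, the by-vaccination summary has no window or assignment rule, and the protocol's SAE/AESI table by preferred term and relationship is not planned

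*SAP*

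**What the plan says.** Protocol 3.6.5.2 says that adverse events are coded and "summarized by part, treatment, vaccination (first or second), and overall". The synopsis has the same wording. SAP 9.1 states that they are "summarized by treatment group as defined in Section 5, vaccination (first or second), and overall", so study part is missing. The SAP names the protocol version of 30 August 2018 as its basis, and the text supplied gives no reason for the difference.

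SAP 9.1 also sets the scope of the tables: "All summary tables (except for the overall summary of AEs) will present SOC and PT", with subject counts and on a treatment-emergent basis. A treatment-emergent event is "any event not present before exposure to study drug or any event already present that worsens in intensity or frequency after exposure", with no end date.

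The SAP does use study part in one place. The overall summary in 9.1.1 has separate Part A and Part B rows for SAEs, related SAEs, deaths, withdrawals and AESIs. It divides the parts by onset: "The AEs in Part B will be the AEs that started after Visit 7".

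Protocol 3.5.6 promises a further output: "A tabulation of all SAEs and AESIs, categorized by the Medical Dictionary for Regulatory Activities (MedDRA) preferred terms and assessed relationship to study drug". SAP 9.1.4 tabulates SAEs by SOC and PT without relationship. For AESIs, SAP 9.1.6 says "All AESIs will be presented in a data listing".

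Protocol 3.5.7.2 says "Any AEs occurring before receipt of the study drug will be analyzed separately from TEAEs".

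**The concern.** The two parts collect different things. Part A records every adverse event up to Visit 7. Part B records only SAEs and AESIs, up to Visit 19 (protocol 3.5.7.6). A SOC/PT table without a split by part adds events from a short period of full collection to events from a long period of selective collection, and its percentages refer to neither. SAEs and AESIs through one year are a primary safety endpoint for Part B, yet no planned table shows them by preferred term separately from Part A.

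The by-vaccination summary has a related gap. Nothing says how long after a dose an event still belongs to that dose, or how an event is assigned to a dose. A late background illness could then appear as a second-dose event, although the first dose had only about four weeks in which to accrue events. That would distort a comparison of first- and second-dose tolerability.

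**Working it through.** The documents give no figure to reproduce, and no sample-size or power calculation bears on this point. The check is a comparison of texts plus arithmetic on the visit schedule.

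**Where the split by part exists**

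- Protocol 3.6.5.2: part, treatment, vaccination, overall.
- SAP 9.1, general rule: treatment, vaccination, overall.
- SAP 9.1.1, overall summary: any-event rows by part.
- SAP 9.1.2 (related events), 9.1.3 (severity) and 9.1.4 (SAEs): treatment and overall, by SOC and PT, with no part.

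With no end date on treatment emergence and no part stratum, the SOC/PT tables as written include Part B events.

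**Vaccination assignment**

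The SAP has no assignment rule. The nearest text is the study-day convention in SAP Section 5, which counts days from the most recent vaccination and has no upper limit. The inputs below are from the visit schedules and count from dose 2 unless stated.

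- Visit 7: Day 28 (+7). Visit 19: Day 364 (+15).
- Dose 1 to dose 2: 28 (+7) days.

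On the nominal schedule, for a subject who receives both doses:

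- Part B length: 364 − 28 = 336 days.
- Part B share of the time after dose 2: 336/364 = 92.3%.
- Second-dose period against first-dose period: 364/28 = 13.0.

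With the visit windows:

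- Visit 7 late: 364 − 35 = 329 days, and 329/364 = 90.4%.
- Visit 19 late: 379 − 28 = 351 days, and 351/379 = 92.6%.
- Ratio of periods: from 364/35 = 10.4 to 379/28 = 13.5.

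So if events go to the most recent dose, more than 90% of the second-dose column's time records only SAEs and AESIs.

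**Size**

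Each dose group has 15 vaccine recipients, and pooled placebo has 3 × 5 = 15.

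- Part B person-time per group: 15 × 336/365.25 = 13.8 person-years.
- The documents give no background SAE rate. At an assumed 2 to 4 per 100 person-years: 13.8 × 0.02 = 0.28 and 13.8 × 0.04 = 0.55 events per group.
- Poisson probability of no event in a group: exp(−0.55) = 58% to exp(−0.28) = 76%.
- One affected subject moves a percentage by 1/15 = 6.7 points.

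**SAE and AESI table**

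| Content | Where in the SAP |
|---|---|
| SAEs by SOC and PT | 9.1.4, no relationship, no part |
| Related SAEs | 9.1.1, one any-event row per part, no PT |
| Related events by SOC and PT | 9.1.2, SAEs not separated |
| AESIs | 9.1.1, one any-event row per part, no relationship; listing in 9.1.6 |
| SAEs and AESIs by PT and relationship | none |

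**Pre-dose events**

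SAEs and AESIs that occur between consent and first dose are recorded. SAP 9.1.1 defines Part A as onset on or before Visit 7, with no lower limit. SAP 9.1 exempts the overall summary from a sentence that sets three properties at once: SOC/PT layout, subject counts and the treatment-emergent basis. The text does not settle whether the last of these still applies to the overall summary.

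**The case against.** Several stronger readings are tempting, and the documents do not support them.

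- *The SAP drops the split by part altogether.* It does not. Section 9.1.1 defines both parts and reports the Part B endpoint with counts and percentages. Only the SOC/PT tables lack the split.
- *Part B events are credited to the second vaccination.* No text says so. The study-day rule numbers days and does not assign events. Sections 9.1.2 to 9.1.4 name no vaccination stratum. The Part A endpoint, 28 days after each dose, supports reading the by-vaccination summary as Part A only. A subject who misses dose 2 is followed from dose 1, up to Day 392, so even a most-recent-dose rule would not always point to dose 2. What stands is that a rule is missing and a programmer would have to guess.
- *AESIs are only listed.* They have an any-event row in each part. SAP 9.1.6 treats them as SAEs, so they should also enter the SAE table, though not marked as AESIs.
- *A pre-dose SAE would count in Part A.* It could. The exemption may mean only that the overall summary has no SOC/PT rows.

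The sponsor could add that protocol 3.6.5.2 itself asks for subject listings of SAEs and AESIs, and that the tabulation sentence sits in a data-collection section. Both statements are in the protocol, however, and a listing does not satisfy the second. The table shells mentioned in SAP Section 5 are not among the documents, so they may already split by part. That cannot be checked, and the SAP text would still differ from the protocol.

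Finally, every SAE and AESI is listed individually, the study has 60 subjects, nothing is formally tested, and comparing dose 1 with dose 2 is not a stated objective. All of this stands and limits the weight of the point.

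**Conclusion.** The point holds as a discrepancy between SAP and protocol, with a small expected effect. The SOC/PT tables lack the part stratum that the protocol requires, and they pool full with selective collection. The by-vaccination summary has no window or assignment rule. The protocol's SAE/AESI tabulation by preferred term and relationship is not planned.

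The 13-fold difference between the dose columns depends on assigning events to the most recent vaccination in two-dose subjects. The 0.28 to 0.55 events per group depends on an assumed rate and full follow-up. A reader might infer that the primary comparison with placebo is biased. It is not: the schedule is the same in all groups and the pooling applies to each alike, provided that retention is similar. What can mislead is the dose-1 versus dose-2 picture and any SOC/PT percentage read as a Part A rate.

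**What to change.** 1. In SAP 9.1, restore study part as a stratum for the SOC/PT tables, using the onset rule already in 9.1.1.
2. Limit by-vaccination adverse-event tables to Part A (28 days after each vaccination, up to Visit 7) and state the assignment rule. It should cover subjects without a second dose, and events between Day 28 and a visit made late within its window.
3. Add one table of SAEs and AESIs by preferred term, relationship, part and treatment, with AESIs identifiable.
4. State in 9.1.1 that the Part A rows count only events starting after the first dose, and list pre-dose events separately as protocol 3.5.7.2 requires.

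The cost is a few sentences in SAP 9.1, 9.1.1, 9.1.4 and 9.1.6 and some extra table shells. No new data are needed.

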#### Vaccine Administration and Dose Escalation Schema

VAL-181388 (or placebo) will be administered as an IM injection (0.5 mL) into the deltoid muscle, preferably in the non-dominant arm, as a 2-dose schedule; the first dose will be given at Visit 1 followed by a second dose 28 days later. VAL-181388 accountability, dose preparation, and administration will be performed by unblinded pharmacy personnel or unblinded designees who will not participate in any other aspect of the study. The remainder of the site staff and all subjects will remain blinded to treatment assignment.

Consent and Screening will occur over a 28-day period prior to randomization. A total of 20 subjects will be randomly assigned to each dose level cohort, 4 subjects (3 VAL-181388 and 1 placebo) to the sentinel safety group and 16 subjects (12 VAL-181388 and 4 placebo) to the expansion group, resulting in 15 subjects being randomly assigned to VAL-181388 and 5 subjects being randomly assigned to placebo (3:1 ratio overall). Subjects meeting all eligibility criteria will receive the first vaccination at Visit 1. Each subject will be monitored in the clinic for at least 1 hour following each vaccination for safety. Assessments will include

vital sign measurements and any immediate reactogenicity. Of note, on the day of vaccination, if a subject is noted to have a systolic or diastolic blood pressure, heart rate, or respiratory rate measurement that shows Grade 2 or higher toxicity after 2 measurements (even after relaxing or resting); has an acute illness; or has an oral temperature  $>38^{\circ}\text{C}$ , the subject should not receive a vaccination on that day and will need to return on subsequent days for their vaccination.

All subjects will return to the clinic at 7 (+3), 17 ( $\pm 3$ ), and 28 (+7) days following each vaccination. In addition, the sentinel safety group will return to the clinic at 1, 2, and 21 (+3) days following the first vaccination. A second vaccination will occur 28 days after the first vaccination (+7 days).

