Should safety laboratory testing result in a Grade 2 or higher toxicity, repeat testing must occur within the next 10 days; this may include an unscheduled visit. Should the subject's laboratory value not return to baseline then periodic testing may be needed until the abnormality is deemed to be associated with a new stable AE or determined to be not clinically significant by the investigator.

Those values that fall within the normal range of the laboratory will automatically be classified as normal. All values that have a toxicity of Grade 1 or higher will also be evaluated by the investigator and classified as “abnormal clinically significant (CS)”, or “abnormal not clinically significant (NCS)”. Investigators should use their clinical judgment when considering the clinical significance of any abnormal laboratory findings. All laboratory test values with a toxicity of Grade 3 or higher will be entered as AEs. Any additional laboratory test value that is determined to be clinically significant will also be recorded as an AE, should that be considered the primary diagnosis. In such instances, the abnormal value and grade will be documented on the AE page of the eCRF. The investigator will continue to monitor the subject with additional assessments until the values have reached the reference range or the values at Screening or until the investigator determines that follow-up is no longer medically necessary. The only exception to this rule would be a laboratory test value that is associated with an identified ongoing AE where that event would be the classifying AE.

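### The overall AE summary can count SAEs and AESIs that began before the first injection as Part A events, although the protocol has pre-dose events analyzed separately

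*SAP*

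**What the plan says.** **SAP 9.1** sets the basis of the AE tables: "except for the overall summary of AEs) will present SOC and PT, will include counts of subjects, and will be based on TEAEs". It defines a TEAE as "any event not present before exposure to study drug or any event already present that worsens in intensity or frequency after exposure". Percentages use the Safety set, which SAP 5.3.3 limits to dosed subjects.

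**SAP 9.1.1** describes the overall summary as numbers and percentages of subjects. Its rows are labelled AE, SAE, AESI and so on; none is labelled TEAE. The boundary between the two parts is: "The AEs in Part A will be the AEs that started on or before Visit 7". Later onsets go to Part B.

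**SAP 9.1.4** also summarizes SAEs by SOC and PT, and under 9.1 that table is TEAE-based. **SAP 9.1.6** treats every AESI as serious and monitors for AESIs from enrollment.

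**Protocol 3.5.7.2** does have a starting point: "In Part A of the study, AEs will be assessed from the time of the first dose administration at Visit 1 through Visit 7". For the time between consent and first dose it says "AEs will only be recorded when they are defined as one or more of the following: SAEs, AESIs, or AEs leading to study withdrawal". It then says: "Any AEs occurring before receipt of the study drug will be analyzed separately from TEAEs". Footnote m of SAP Table 13-1 repeats the recording rule, but the SAP plans no separate pre-dose summary or listing. Such events would appear only in the general AE, SAE and AESI listings.

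**Protocol 3.1** gives the length of the pre-dose period: "Consent and Screening will occur over a 28-day period prior to randomization".

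**Protocol 3.5.8** adds a laboratory rule, repeated in SAP 9.2: "All laboratory test values with a toxicity of Grade 3 or higher will be entered as AEs".

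**The concern.** Safety relative to placebo is the primary objective, and the overall AE summary is the table most readers will look at first. An event that began before any injection cannot be an effect of the vaccine or of the placebo. If it is counted as a Part A event, three things follow:

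- The row no longer describes post-exposure safety.
- The SAP departs from the protocol's instruction on pre-dose events.
- The summary and the SOC/PT tables can show different numbers for what looks like the same quantity.

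Randomization balances pre-dose events only on average. In groups this small, a single event on one side is visible.

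**Working it through.** The plan states no figure on this point, so there is none to reproduce. The check is a comparison of the texts, followed by the size of one event.

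**1. Does the Part A rule leave pre-dose onsets anywhere else to go?** Part A is onset up to and including Visit 7, and Part B is onset after it. Together the two cover all time. A recorded pre-dose onset therefore falls in Part A unless some other rule removes it.

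**2. Does another rule remove it?** Only a TEAE basis for this table would. SAP 9.1 can be read in two ways:

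- The exception covers the whole sentence. The overall summary is then not TEAE-based, and pre-dose onsets stay in.
- The exception covers only the SOC/PT layout. The summary is then meant to be TEAE-based, and pre-dose onsets drop out.

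The SAP does not say which is meant, and the row labels and boundary in 9.1.1 do not settle it.

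**3. Which pre-dose events are in the database?** Under Protocol 3.5.7.2, only SAEs, AESIs and AEs leading to withdrawal. A subject who withdraws before dosing is not in the Safety set. What remains is an SAE or AESI in a subject who is still dosed.

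**4. Trace one such event.** Take an SAE that begins on the tenth day of screening and does not worsen after dosing.

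| Place | Treatment of the event |
|---|---|
| SAP 9.1.1, Part A SAE row as written | counted |
| SAP 9.1, TEAE definition | not a TEAE |
| SAP 9.1.4, SAE table by SOC and PT | not counted |
| Protocol 3.5.7.2 | kept apart from TEAEs |

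An AESI would enter both the SAE and the AESI rows, because SAP 9.1.6 makes it serious. Either event might also enter the rows for any unsolicited, Grade 3 or 4, or medically attended AE. Treatment-related rows should be unaffected.

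**5. Size of one event.** Each cohort has 20 × 3/4 = 15 vaccine and 20 × 1/4 = 5 placebo subjects. Pooled placebo is 3 × 5 = 15, so every group has n = 15. Exact (Clopper-Pearson) 95% limits:

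- 0/15 = 0%; upper limit 1 − 0.025^(1/15) = 21.8%.
- 1/15 = 6.7%; lower limit 1 − 0.975^(1/15) = 0.2%; upper limit, the 97.5th percentile of Beta(2, 14), = 31.9%.

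A difference from pooled placebo, of the kind planned in Protocol 3.6.5.2, shifts by 6.7 percentage points. If the table is TEAE-based, the contribution of such an event is 0 in every group.

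**6. Laboratory values (secondary).** Visit 1 safety samples are drawn before dosing (Protocol Table 6-1). The rule in Protocol 3.5.8 would make any Grade 3 or higher value an AE. Protocol 3.5.7.2 would not record it before dosing unless it is also an SAE, an AESI or a cause of withdrawal. The documents do not say which rule prevails.

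**The case against.** The strongest reply is that the exception in SAP 9.1 concerns layout only. Read as covering the whole sentence, it would also excuse the overall summary from counting subjects, yet 9.1.1 says that it does count them. This argument stands: a reader might infer that the SAP deliberately waives the TEAE basis, and the documents do not support that. What they support is that the basis is left unclear.

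It can also be said that the Visit 7 sentence was written to divide Part A from Part B, and that the start is given elsewhere. SAP Table 13-1, footnote m, starts AE assessment at Visit 1 dosing, and SAP 4.2 ties unsolicited AEs to the 28 days after each vaccination. That weakens the case for the unsolicited rows. It does not help the SAE and AESI rows, because the same footnote has those events recorded from consent.

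The reply on numbers also stands. Exclusions 10 and 12 in Protocol 3.2.2 (autoimmune and neurologic conditions), together with 1 and 22, would keep many subjects with a screening AESI from being dosed.

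Two stronger readings are tempting:

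- *SAE and AESI counts would be inflated by 40 to 50%.* This sets 28 screening days against 56 to 70 post-dose days (28/70 = 40%, 28/56 = 50%). It assumes full-length screening, a constant event rate and that every affected subject is dosed. Eligibility and the Safety set contradict the last assumption.
- *Abnormal Visit 1 laboratory values would regularly enter the summary.* The pre-dose recording limit speaks against this, and the documents give no rate from which to calculate a probability.

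Finally, the protocol asks for separate analysis, not for a particular table, and SAP Section 5 assigns pre-dose study days, so most pre-dose events can be found in the listings. That is true, but it does not correct the headline count.

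**Conclusion.** The concern holds in limited form. The SAP does not clearly make the overall AE summary treatment-emergent, and its Part A rule has no lower bound. A pre-dose SAE or AESI in a subject who is later dosed is therefore counted in Part A as 9.1.1 is written, in conflict with Protocol 3.5.7.2 and potentially with the SAP's own SOC/PT tables.

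Few events are likely, possibly none. The documents give no pre-dose rate, so no expected number is claimed. The effect per event is 6.7 percentage points in a group of 15, assuming the planned group sizes are reached and the subject has no other event in that row. The conflict between the laboratory rule and the pre-dose recording limit is real but secondary; the point does not depend on it.

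**What to change.** - **SAP 9.1:** state that the overall summary is exempt only from the SOC/PT layout and is based on TEAEs.
- **SAP 9.1.1:** define Part A as onset or worsening from the first injection through Visit 7. Worsening must be named, because a limit on onset date alone would lose pre-existing events that become TEAEs.
- **Pre-dose listing:** show SAEs, AESIs and AEs leading to withdrawal before the first injection separately, in line with Protocol 3.5.7.2.
- **Visit 1:** reconcile the Grade 3 laboratory rule with the pre-dose recording limit, and classify abnormalities from pre-dose assessments as not treatment-emergent. The study-day formula in SAP Section 5 works by date and cannot separate the two sides of a same-day dose, so use time of dosing and time of onset or sampling.

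The cost is SAP wording, one programming condition and one short listing. No new data are needed: dose date and time are recorded under Protocol 3.4.6, and AE onset time under 3.5.7.3. The only downside is that some headline counts may be slightly lower.
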